Statement of problem: There is a strong crossway relationship between periodontitis and hypertension. Hypertension is the most prevalent of cardiovascular diseases and its prevalence is increased by the presence of periodontitis. Periodontal attachment loss is higher in hypertension patients when compared to healthy subjects. Both are examples of non-communicable diseases (NCDs), also known as chronic inflammatory diseases, they tend to be of long duration and are the result of a combination of genetic, physiological and environmental factors. The lack of an appropriate balance between these factors results in cellular changes as well as the levels of cytokines with subsequent changes in clinical manifestations of periodontal diseases. Both periodontitis and hypertension are associated with inflammation and an increase in specific proinflammatory cytokines.

Aim of the study: To investigate the correlation between the clinical parameters and the levels of Endocan and TNF- α in gingival crevicular fluid (GCF) before and after non-surgical periodontal therapy (NSPT) in stage II periodontitis patients with hypertension in comparison to non-hypertensive patients.

Materials and Methods

Clinical assessment of specific clinical parameters: plaque index, gingival index, probing depth, clinical attachment level (CAL) as primary outcome. Biochemical assessment of Endocan and TNF- α levels in GCF by Enzyme Linked Immunosorbent Assay (ELISA) as well as measurement of blood pressure at baseline and after 3 months as secondary outcomes.

II. Background:

Hypertension and periodontitis are part of a group of diseases called non-communicable diseases (NCDs), which are rising in prevalence due to an increasingly aging population. NCDs comprise 71% of global death.

Hypertension is defined as repeated office SBP values ≥ 140 mmHg and/or DBP ≥ 90 mmHg. It is a multifactorial disease, that can be caused by endothelial dysfunction (ED), oxidative stress, and inflammation. Periodontitis is a chronic multifactorial inflammatory condition affecting the tooth periodontium. In periodontitis, chronic inflammation occurs in reaction to untreated bacteria, and this is associated with continuous stimulation of the immune system which subsequently causes damage to the tooth supporting tissues. The damage is manifested clinically with gingival bleeding, foul odor, clinical attachment loss, tooth mobility and may lead eventually to tooth loss.

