“What is the effect of NSPT on the clinical periodontal parameters and its correlation to changes in GCF levels of Endocan and TNF- α in hypertensive periodontitis patients compared to non-hypertensive patients?”

PICOTS Elements:	
Patient/Problem	Stage II periodontitis patients with controlled hypertension.
Intervention	Non-Surgical periodontal therapy.
Comparator	Stage II periodontitis healthy individuals.
Outcome	-Clinical evaluation as a primary objective. -Biochemical evaluation as secondary objective. -Blood pressure measurement as secondary objective.
Time	-Baseline and 3 months (for clinical evaluation) -3 months (for biochemical analysis) -3 months (for blood pressure evaluation)
Setting	Faculty of Dentistry, Ain Shams University.

IV. Aim of the Study:

- 1- To correlate changes in GCF level of Endocan and TNF- α with changes in periodontal parameters after NSPT in both groups with clinical parameters.
- 2- The aim of the present study is to investigate changes in the levels of Endocan and TNF- α in stage II periodontitis patients with controlled hypertension in comparison to healthy subjects before and after NSPT.
- 3- To correlate blood pressure changes before and after NSPT.

Primary outcome:

Clinical evaluation of periodontal parameters plaque Index, gingival index, probing depth and clinical attachment level comparing between hypertensive and non-hypertensive groups.

Secondary outcome (s):

- Biochemical evaluation of GCF levels of Endocan and TNF- α in hypertensive and healthy subjects by ELISA.
- Systolic and Diastolic Blood pressure measurements before and after NSPT in hypertensive vs healthy individuals and check if NSPT reduces SBP and DBP.

Clinical Relevance:

To understand the role of NSPT in stabilizing the periodontal condition as well as reduce GCF levels of Endocan and TNF- α which will subsequently result in better hypertension control and improve the lifestyle.

V. Hypothesis:

Hypertension influences response to NSPT and GCF levels of Endocan and TNF- α .

VI. Ethical considerations

•Risk and discomfort of patients: This research will be conducted with considerations of patients' safety and with attempts to reduce patients' discomfort by reassurance.

•Minimization of the risk: Patients' baseline vitals will be taken before any clinical intervention to ensure patients' safety. Moreover, all medical operations will be conducted under standardized infection control

procedures.

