- **Criteria for Discontinuation of Study/patient:** Patients will be allowed to leave the study if he/ she didn't conform with the oral hygiene instructions, this will be ensured by 2 weeks, 4 weeks and 6 weeks follow-up after NSPT and assessing clinical parameters like Plaque index (PI) to determine how compliant is the patient with oral hygiene instructions. Patients with PI 2 will be eliminated. Patients with uncontrolled hypertension (SBP greater than or equal to 140mmHg and DBP greater than or equal to 90mmHg) will be eliminated.
- **Benefits to the Patients and to the Community:** Patients will receive NSPT and oral hygiene instructions with no cost. The community will benefit from this study by having a better diagnostic modality for moderate cases of periodontitis and preservation of dentition. NSPT is expected to improve patients' oral/overall health and quality of life and to be of relevance in the management of patients with hypertension.
- **Privacy:** All patients' identification including patient data and photographs will be locked and not shared.
- **Confidentiality:** Patient's data will be treated with utmost confidentiality. No personnel other than the researchers will have access to the patients' data.
- **Data Management:** All patients' data will be saved on researcher's personal laptop that are not connected to any internet connections and no copies will be made in any kind of database.
- **Consent Procedures if Applicable:** Any medical procedures and photographs will have a printed written consent form.
- **Patient Informed Consent Form:** A proper consent form will be formulated & signed by the patient before starting any procedure.

VII. Study Design:

Case-control study.

VIII. Materials and Methods:

- **Study Setting:** Faculty of Dentistry, Ain Shams University.
- **Sample Size Calculation:**

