A power analysis was designed to have adequate power to apply a two-sided statistical test of the null hypothesis that there is no difference would be found between tested groups regarding clinical evaluation. By adopting an alpha (α) level of (0.05), a beta (β) of (0.2) (i.e., power=80%) and an effect size (d) of (1.53) calculated based on the results of a previous study; the total required sample size (n) was found to be (26) cases. Total sample size was increased by (25%) to account for possible dropouts during follow-up intervals to be (34) cases (i.e., 17 cases per group). Sample size calculation was performed using G*Power version 3.1.9.7. Increase to 20 cases per group to compensate for dropouts. (28)

- **Eligibility criteria:**

Inclusion Criteria

1. Patients with stage II periodontitis and controlled hypertension (self-reported history of a diagnosis of HTN by a physician and blood pressure (SBP < 140 and DBP < 90).
2. Both genders aged from 30-70.
3. Minimum 20 natural teeth excluding third molars.
4. Good compliance with the plaque control instructions following initial therapy.
5. Availability for follow-up and maintenance program.

Exclusion criteria:

1. Smokers.
2. Pregnant and lactating females.

3. Patients with other systemic diseases, such as diabetes mellitus, rheumatoid arthritis and cancer.
(According to Cornell Medical Index-Health Questionnaire).
4. Patients taking antibiotic, anti-inflammatory, and immunosuppressive therapy during the preceding 3 months before the start of the trial and during the study.
5. Patients who have undergone any periodontal therapy in the last 6 months.

Justification for Exclusions:

To reduce any confounding factors and bias that may affect the results of this study.

Study procedures:

1- Details of the interventions, testing and follow up:

Group Case (I):

This group will include 20 patients diagnosed with stage II periodontitis and controlled hypertension. They will receive NSPT and oral hygiene measures will be instructed following treatment.

Group Control (II):

This group will include 20 patients diagnosed with stage II periodontitis and no hypertension. They will receive NSPT and oral hygiene measures will be instructed following treatment.

Study protocol and surgical steps:

1. Before enrollment, a detailed case history will be recorded.

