2. A calibrated standard aneroid sphygmomanometer. The average of 3 blood pressure values (systolic blood pressure SBP and diastolic blood pressure DBP), will be taken at 1 minute interval, this will be used in data analyses.

(2020 International Society of Hypertension Global Hypertension Practice Guidelines)

3. For all patients who are suitable for the study the following clinical evaluation parameters will be measured:
 - a) Plaque index (PI) (Silness&Löe, 1964)
 - b) Gingival index (GI) (Löe&Silness, 1963)
 - c) Probing depth (PD) (Caton, 1980).
 - d) Bleeding on probing (BOP) (Ainamo, 1985)
 - e) Clinical attachment level (CAL) (Ramfjord, 1967).
 - f) Standardized periapical radiograph. (Pananou, 2017)

Note: Full mouth assessment will be done and then the deepest site will be evaluated for the GCF sample.

4. Baseline GCF samples will be taken the day after patients were clinically evaluated to prevent contamination with blood related to the probing of inflamed areas.
5. The sample areas will be insulated with cotton rolls to prevent saliva contamination and all supragingival plaque will be eliminated. The paper strips will be placed into the periodontal pocket and then permitted to remain for 30 seconds.
6. All patients will undergo full mouth NSPT, this will be done using ultrasonic and hand instruments.
7. The patients will receive oral hygiene instructions including tooth brushing using modified bass technique. All patients will be provided with toothbrush (soft), toothpaste (signal) and interdental cleaning with dental floss or interdental brush.
8. Two weeks follow-up to ensure that appropriate oral hygiene instructions are followed. The clinical parameter to be assessed will be PI and BOP, patients with PI 2 and BOP $> 10\%$ will be eliminated from the study.
9. Then clinical evaluation, collection of samples and measuring of SBP and DBP will be performed at 3 months after NSPT in both groups.

Outcomes Assessment:

- Clinical assessment.
- Biochemical assessment.
- Blood pressure measurement.

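### The blood pressure objective asks whether NSPT lowers pressure although every patient receives NSPT, and the pressure-based elimination rule names no visit and does not match the entry rule (minor; secondary outcome)

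*Protocol*

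**What the plan says.** Five places in the protocol bear on this point.

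- **Objective.** Section IV lists systolic (SBP) and diastolic (DBP) pressure as a secondary outcome, measured before and after NSPT, "in hypertensive vs healthy individuals and check if NSPT reduces SBP and DBP". Under Clinical Relevance it expects NSPT to reduce the two biomarkers, "which will subsequently result in better hypertension control and improve the lifestyle".
- **Treatment.** Section VIII gives NSPT to the 20 hypertensive and the 20 non-hypertensive patients alike. No group goes without it or receives it later.
- **Entry.** Inclusion criterion 1 (section VIII) requires a physician's diagnosis of hypertension "and blood pressure (SBP < 140 and DBP < 90". The Background (section II) uses the same limits differently joined: "Hypertension is defined as repeated office SBP values ≥ 140 mmHg and/or DBP ≥ 90 mmHg".
- **Elimination.** Section VI, under the criteria for discontinuation, says: "Patients with uncontrolled hypertension (SBP greater than or equal to 140mmHg and DBP greater than or equal to 90mmHg) will be eliminated". No visit is named. The sentence follows directly on the plaque-index eliminations tied to the 2-, 4- and 6-week visits.
- **Schedule.** Under Outcomes Assessment, the 2-, 4- and 6-week visits record plaque index and bleeding on probing only. Pressure is measured before NSPT and at 3 months. Step 2 of the study procedures averages three readings, which "will be taken at 1 minute interval, this will be used in data analyses". Step 3 then begins "For all patients who are suitable for the study the following clinical evaluation parameters will be measured".

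**The concern.** There are two separable problems, both in text that the protocol itself fixes.

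First, the pressure objective is worded as a treatment-effect question, and the design has no contrast in treatment. A fall in pressure could be read as evidence that NSPT lowers it or improves hypertension control, which this study cannot show. An analysis plan could not supply the missing comparator.

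Second, the elimination rule leaves open whether a 3-month reading can remove a patient who has been treated and followed to the end. If it can, patients are selected on the value of a secondary outcome. The word used is *eliminated*, with no limit to the pressure analysis, so it is also unclear whether those patients' clinical and biochemical data would be kept.

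**Working it through.** **1. What the pressure comparison can estimate.** Write the mean change in group g (hypertensive H, control C) as

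change(g) = NSPT effect(g) + other before-after influences(g),

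where the second term holds medication changes, repeat measurement and regression to the mean. No group has NSPT effect = 0 by design, so the two terms cannot be separated within a group. The difference change(H) − change(C) is the difference in NSPT effect plus the difference in other influences. It is not the effect of NSPT.

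**2. The two rules side by side.**

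- Entry: SBP <140 and DBP <90. Its complement is SBP ≥140 *or* DBP ≥90.
- Elimination: SBP ≥140 *and* DBP ≥90.
- A patient at 150/85 or 135/95 fails entry but does not meet the elimination rule.

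**3. When the rule can act.** Before NSPT, the entry rule already excludes every hypertensive patient whom it would catch, so it is redundant. At 2, 4 and 6 weeks no pressure is scheduled. That leaves 3 months, where the reading is the outcome.

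**4. Size if applied at 3 months.** The protocol gives no pressure means, SDs or correlations, so there is no figure of its own to reproduce and all inputs here are assumed. Hypertensive patients before screening average 130/80 or 134/84; between-person SD is 10/7; visit-to-visit SD is 8/5; the SBP-DBP correlation is 0.5 or 0.6; the NSPT effect is zero. Two million patients were simulated per case. Those entering have a first reading <140 and <90, and that reading is taken as baseline.

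| Pre-screening mean, correlation | Removed by *and* | Chance of ≥1 of 20 | Mean SBP change, all kept | After *and* rule | Shift | Removed by *or* |
|---|---|---|---|---|---|---|
| 130/80, 0.5 | 2.6% | 0.41 | +2.04 | +1.66 | −0.38 | 16.8% |
| 130/80, 0.6 | 3.1% | 0.47 | +2.05 | +1.60 | −0.45 | 16.2% |
| 134/84, 0.5 | 5.3% | 0.66 | +2.88 | +2.15 | −0.73 | 25.0% |
| 134/84, 0.6 | 6.0% | 0.71 | +2.89 | +2.05 | −0.84 | 23.9% |

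Expected removals under *and* are 20 × 0.026 = 0.5 to 20 × 0.060 = 1.2 patients. The chance of at least one is 1 − (1 − p)^20; for p = 0.026 this is 1 − 0.974^20 = 0.41. Over a wider grid (pre-screening means 126/78 to 134/84, SBP person SD 8–12, SBP visit SD 6–10, correlation 0.4–0.7) the shift runs from −0.06 to −1.8 mmHg. A separate parametrisation (means 128/80 to 135/85, total SD 12/8, 3-month correlation 0.6–0.75) gives 2–7% removed and a shift of −0.2 to −1.0 mmHg.

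**5. Scale.** With 20 patients and an SD of change of 10.5–11 mmHg, the 95% half-width is t(19) × SD/√20: 2.093 × 10.5/4.472 = 4.9 and 2.093 × 11/4.472 = 5.15 mmHg.

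**6. Regression to the mean.** The positive changes with all patients kept come from the entry ceiling alone. They arise only if the eligibility reading is also the analysis baseline. On the same inputs a true SBP change of −5 would appear as about −3.0 to −2.1.

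**The case against.** The best defence of the rule is that it was meant as a baseline screen. Section VI says that patients' "baseline vitals will be taken before any clinical intervention", the cut-offs are those of the entry criterion, and 3 months is the last scheduled visit, when nothing is left to discontinue. On that reading it does no harm, and the *and* is probably a slip. Nor need a withdrawal limit mirror an entry limit. This is plausible and lowers the weight of the point. It does not remove it, because the text names no visit and places the rule among post-treatment eliminations.

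A second defence is that analysis sets are commonly left to the analysis plan, and that *eliminated* need not mean that collected data are discarded. That also stands. A reader might infer that treated patients' clinical and biochemical data will be deleted, but the protocol does not say so. It leaves the matter open.

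Third, losses are small and allowed for: the protocol raises a calculated 26 patients in total to 20 per group for dropouts.

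A reader might also infer that the rule would manufacture an apparent benefit. The figures do not support this. If the eligibility reading is the baseline, the entry ceiling pushes later pressure upward, against a false claim of benefit, and the rule offsets part of that drift (for example +2.04 becomes +1.66). That does not justify selecting on an outcome. The drift itself depends on the step 2 reading deciding eligibility, which the step order suggests and the text does not state.

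Finally, better hypertension control appears under Clinical Relevance and is not an endpoint, and treating both groups suits the main hypothesis about hypertension and response. Both are correct. The objection to the objective is to its causal wording only.

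**Conclusion.** The point holds as a minor one on a secondary outcome.

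That a pressure change cannot be attributed to NSPT follows from the design and needs no assumed figures. The same is true of the missing visit, the *and*/*or* mismatch, and the fact that the only scheduled post-treatment pressure is the outcome itself. A change by group, and a difference in change between groups, can still be described. It would go too far to say that the pressure data are uninformative or that the design is wrong.

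The numerical harm of the rule as written is small: about 1 of 20 hypertensive patients and less than 1 mmHg in mean SBP change in the base cases, up to 1.8 mmHg at the edge of the wider grid. Those sizes rest wholly on assumed inputs and on the rule being applied at 3 months, which the protocol neither says nor rules out.

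**What to change.** 1. Restate the pressure objective in section IV as a descriptive before-after change in each group and a between-group difference in change. Draw no conclusion that NSPT lowers pressure or improves hypertension control.
2. In section VI, state that the pressure rule applies at screening, before NSPT only, and word it as SBP ≥140 or DBP ≥90 to match entry. Add that no treated patient is removed from any analysis because of a later reading, and that such patients are referred for medical care. The two changes belong together: *or* applied at 3 months would remove about 16–25% of the hypertensive group (3–5 of 20) on the assumed inputs.
3. If the eligibility reading also serves as baseline, name regression to the mean from the entry ceiling as a limitation: an upward drift that attenuates any fall.

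The cost is wording and a weaker pressure claim. No patients, visits or measurements are added.

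### The stated effect size (d = 1.53), power (80%) and required total (26) do not agree: those inputs need 16 patients, and the clinical parameter behind d is not named

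*Protocol*

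**What the plan says.** Section VIII of the protocol (Sample Size Calculation) describes a "two-sided statistical test of the null hypothesis" that "no difference would be found between tested groups regarding clinical evaluation". The inputs are given as "By adopting an alpha (α) level of (0.05"), "a beta (β) of (0.2) (i.e., power=80%) and an effect size (d) of (1.53"), the last taken from a previous study. From these, "the total required sample size (n) was found to be (26) cases". A 25% increase for dropout brings the total to 34, or 17 per group, and the paragraph names G*Power 3.1.9.7 as the software. It then adds a further step: "Increase to 20 cases per group to compensate for dropouts". The group descriptions in the same section confirm 20 patients in each group.

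Section IV gives the primary outcome as "Clinical evaluation of periodontal parameters plaque Index, gingival index, probing depth and clinical attachment level comparing between hypertensive and non-hypertensive groups". The Time row of the PICOTS table in section III reads "Baseline and 3 months (for clinical evaluation").

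**The concern.** A standardised difference of 1.53 is very large, and 13 patients per group looks too many for 80% power against it. If the stated inputs do not lead to 26, at least one of d, power and N is misreported, and the reader cannot tell what effect the study was designed to detect.

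A value of d also belongs to one variable at one time point, or to one change score. The paragraph attaches it only to clinical evaluation in general, while the primary outcome comprises four parameters at two time points. Without the parameter, or the mean difference and standard deviation behind d, the calculation cannot be checked against its source. Nor can anyone say which part of the primary outcome it supports.

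**Working it through.** **Inputs, all from the sample size paragraph in section VIII:** two-sided alpha 0.05; power 0.80; d = 1.53; 1:1 allocation (17 per group, then 20 per group); stated requirement 26, that is 13 per group.

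**Method.** The paragraph names no test, so I start with the two-sample t-test and its exact power. With n per group, the degrees of freedom are 2n − 2 and the noncentrality is d × √(n/2). Power is the probability that a noncentral t variable exceeds the two-sided 5% critical value; the opposite tail is negligible here.

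**Step 1: try to reproduce 26.**

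- n = 7: noncentrality 1.53 × √3.5 = 2.862, critical value 2.179 on 12 df, power 74.8%.
- n = 8: noncentrality 1.53 × √4 = 3.06, critical value 2.145 on 14 df, power 81.2%.

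The smallest size reaching 80% is 8 per group, so **16 in total**. The stated figure is not reproduced: 26 − 16 = 10 patients more, and 10/16 is about +62%.

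**Step 2: power at other sizes, d = 1.53.**

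| n per group | Total | Power |
|---|---|---|
| 8 | 16 | 81.2% |
| 11 | 22 | 92.7% |
| 12 | 24 | 94.7% |
| 13 | 26 | 96.2% |
| 17 | 34 | 99.1% |
| 20 | 40 | 99.7% |

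**Step 3: which single change to the t-test inputs gives 26?**

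- *Power target.* At d = 1.53, an 80% target needs 16, 90% needs 22 and 95% needs 26 (12 per group falls just short at 94.7%; 13 gives 96.2%).
- *Effect size.* At 80% power, 13 per group is enough from d = 1.1454 and 12 per group from d = 1.1968. So 26 is the answer for d from about 1.146 (13 per group: 80.04%) to 1.196 (12 per group: 79.95%).

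**Step 4: other readings at d = 1.53 and 80% power.**

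- Mann-Whitney, two-sided 0.05: 9 per group (18) with the normal-theory asymptotic relative efficiency (ARE) of 0.955; 10 per group (20) with the minimum ARE of 0.864.
- One-sided t-test: 14. Paired t-test: 6. Neither matches the stated two-sided comparison of groups.
- Unequal allocation at 4:1: 25, but the protocol has equal groups.
- Alpha split over four parameters, 0.05/4 = 0.0125: t-test 24. Mann-Whitney with minimum ARE gives 13 per group, so 26 (power 80.2%).

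No reading that keeps all the stated inputs gives 26.

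**Step 5: from 26 to 40.** The first increase follows from the text: 13 × 1.25 = 16.25, rounded up to 17 per group, 34 in total. The final figure is 40/26 − 1 = 54% above 26. Put the other way, 1 − 26/40 = 35% can be lost before fewer than 26 remain, provided that 13 of 20 remain in each group.

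**Step 6: what does d describe?** Section VIII says only clinical evaluation. Section IV lists plaque index, gingival index, probing depth and clinical attachment level, and section III has baseline and 3 months. Nothing links 1.53 to one of the four, or to a 3-month value rather than a change.

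**The case against.** **The test is not named.** Plaque and gingival index are ordinal 0–3 scores, so a rank test is plausible and 16 is the low end of the range. This stands in part: with Mann-Whitney the answer is 18 to 20, and the excess is 6 to 8 patients (30% to 44%). That still does not reach 26.

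**An alpha split over the four primary parameters, combined with Mann-Whitney at minimum ARE, gives exactly 26.** The arithmetic is right. But it requires a split and a test that the paragraph does not mention, and the paragraph states alpha as 0.05. It may be what was done; it is not what is written.

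**The parameter may be identifiable.** The opening summary can be read as making attachment level the primary outcome, and the paragraph cites a reference for the calculation. The summary wording is ambiguous, though, and section IV lists four parameters without ranking them. A citation does not say which of its results was used. A separate analysis plan might name the parameter and time point, but the protocol is where this calculation is presented as justified.

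**The consequence is small, and the assurance about enrolment is conditional.** The first part is true: the discrepancy is conservative and no design decision changes. On the second, 20 per group gives 80% power down to d of about 0.91, so 40 is safe under either correction in Step 3 but not for every value the source might show. The 35% tolerance also assumes balanced loss. Discontinuation for uncontrolled hypertension (section VI) may fall more on the hypertensive group.

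**Conclusion.** The concern holds. At the stated inputs the requirement is 16 patients by t-test (18 to 20 by Mann-Whitney), against 26 stated; and 26 patients have 96.2% power at d = 1.53, not 80%. At least one of the stated figures is wrong, or an input was used that is not stated. The exact match at a 95% power target is suggestive, but the document does not confirm it.

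The study is not underpowered for its stated effect: 20 per group gives 99.7% at d = 1.53. If d was really about 1.146, 26 evaluable patients still give 80%. What fails is the justification: a reader cannot tell whether the planned effect was 1.53 or about 1.15 to 1.20 standard deviations, or on which parameter. This should be corrected, but it does not threaten the study.

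The result rests on equal groups, a single comparison at two-sided 0.05, and the usual t-test or ARE-based power formulas.

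**What to change.** Retrieve the source study's values and the saved G*Power output, and rewrite the paragraph so that d, power and N agree. Depending on what those records show, the consistent t-test statements are:

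- d = 1.53, 80% power, N = 16;
- d = 1.53, 95% power target (about 96% achieved), N = 26;
- the corrected d (about 1.146 to 1.196) with 80% power, N = 26.

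The choice must come from the records, not from whichever option fits best. If a rank test or an adjusted alpha was used, state it. Name the one clinical parameter and time point (or change) that d describes, and give the mean difference and standard deviation behind it.

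Keep enrolment at 40, 20 per group. Replace the two successive dropout increases with one statement: going from 26 evaluable to 40 enrolled is a 54% increase and allows a loss of up to 35%, if 13 remain in each group. If the source shows a d below about 0.91, the adequacy of 40 would have to be looked at again.

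The cost is one reworded paragraph. The only downside is that a smaller assumed effect must be declared if the source shows one.

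### Case status rests on an unverified self-reported diagnosis that entry blood pressure cannot confirm, and changes in antihypertensive treatment over the 3 months are not captured

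*Protocol*

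**What the plan says.** All references are to the protocol.

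- **Cases.** Section VIII, Eligibility criteria, inclusion criterion 1 admits "Patients with stage II periodontitis and controlled hypertension (self-reported history of a diagnosis of HTN by a physician", together with "blood pressure (SBP < 140 and DBP < 90". It asks for no medical record, prescription or current treatment.
- **Controls.** Section VIII, Study procedures, Group Control (II): "This group will include 20 patients diagnosed with stage II periodontitis and no hypertension". No pressure limit or method of establishing this is given.
- **Definition of the disease.** Section II, Background: "Hypertension is defined as repeated office SBP values ≥ 140 mmHg and/or DBP ≥ 90 mmHg".
- **What is collected at entry.** Step 1 of the study steps reads "Before enrollment, a detailed case history will be recorded", without listing the items. Step 2 averages three pressure readings taken one minute apart.
- **Drugs.** Exclusion criterion 4 names antibiotic, anti-inflammatory and immunosuppressive therapy. Antihypertensive drugs are named nowhere in the protocol.
- **Blood pressure as an outcome.** The secondary outcomes in section IV ask whether NSPT lowers systolic and diastolic pressure. Section VIII, Outcomes Assessment, measures pressure before NSPT and 3 months after it.
- **Discontinuation.** Section VI removes patients with uncontrolled hypertension, defined as systolic at or above 140 mmHg *and* diastolic at or above 90 mmHg.

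**The concern.** The hypothesis in section V is that "Hypertension influences response to NSPT" and the two crevicular fluid markers. Hypertension status is therefore the one factor that every between-group comparison depends on. A case must read below 140/90 at entry, and so will a control who is truly free of hypertension. The measured pressure does not tell them apart. The stated history does, and nothing checks it. Someone once told of a high reading, never treated and now reading 122/78, meets criterion 1.

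Two things are at stake. Cases who are not truly hypertensive would dilute the between-group differences in clinical parameters, markers and pressure. Separately, antihypertensive drugs can be started, stopped or adjusted during follow-up, almost only in cases. With no record of this, the resulting pressure change would be read as an effect of NSPT.

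Both are matters of eligibility and data collection. No later analysis can recover a diagnosis that was not verified or a drug change that was not noted.

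**Working it through.** **1. Can entry pressure confirm case status?** The Background definition needs repeated values at or above 140 and/or 90. Criterion 1 needs values below both limits. A case therefore cannot show hypertension, as the Background defines it, on the entry readings. The confirmation has to come from somewhere else, and the only source named is self-report.

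**2. Dilution.** Let H be the mean response of truly hypertensive patients, N that of the others, and p the fraction of labelled cases who are not truly hypertensive and respond like controls.

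- Case mean = (1 - p)H + pN; control mean = N.
- Expected difference = (1 - p)H + pN - N = (1 - p)(H - N).

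The documents give no value of p, so a range is assumed: p = 10% leaves 90% of the true difference, 20% leaves 80%, and 30% leaves 70%. With 20 cases these are 2, 4 and 6 patients.

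**3. What this does to power.** The inputs from section VIII, Sample Size Calculation, are d = 1.53, two-sided alpha 0.05, power 80%, a stated total of 26 (13 per group), 34 after a 25% increase, and finally 20 per group.

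The plan's own figure comes first. An exact two-sample t-test with d = 1.53 and 80% power needs 8 per group, or 16 in total, not 26. Thirteen per group is what a 95% target gives (actual power 96.2%). This mismatch is a separate matter and errs towards a larger study, but it explains why power has room to spare here.

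Under the mixture, with within-group SD of 1, the case variance is 1 + p(1 - p) × 1.53². The diluted effect size is (1 - p) × 1.53 / √{[2 + p(1 - p) × 1.53²]/2}. For p = 20% this is 1.224 / √(2.3745/2) = 1.224 / 1.090 = 1.12.

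| p (assumed) | Difference retained | Diluted d | Power, 13 per group | Power, 20 per group |
|---|---|---|---|---|
| 0% | 100% | 1.53 | 96% | 99.7% |
| 10% | 90% | 1.31 | 89% | 98% |
| 20% | 80% | 1.12 | 79% | 93% |
| 30% | 70% | 0.96 | 65% | 84% |

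**4. Drug changes and the pressure outcome.** Spurious mean shift in cases = share of cases with a change × mean effect of the change. Neither figure is in the documents. Assuming 10% to 30% of cases and 5 to 10 mmHg, the shift runs from 0.10 × 5 = 0.5 mmHg to 0.30 × 10 = 3 mmHg.

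**5. The pressure limits side by side.** The Background joins the two limits by *and/or*. Criterion 1 requires both values below the limits. The discontinuation rule in section VI requires both values at or above them. A patient persistently at 150/85 meets the Background definition and fails criterion 1, yet is not removed by section VI as written. These statements must be reconciled.

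**The case against.** The strongest reply is that the population is controlled hypertension by design. The PICOTS table, the second aim and criterion 1 all say so. Similar entry pressure in the two groups is then intended and is no defect in itself. That stands. The weakness is only that, with pressure unable to serve as a check, nothing else takes its place.

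A reader might infer that antihypertensive treatment goes wholly unrecorded. The protocol does not support that. A detailed case history is taken before enrolment, and other systemic diseases are screened with a health questionnaire, so baseline drugs may well be noted. What can be said is that they are not a specified item and that later changes are not captured.

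A reader might also infer that controls are misclassified to a similar degree, for example those reading just under the limits. Under the Background definition such a reading is not hypertension. Controls also have their pressure measured and their history taken, so there is little basis for putting a figure on error in that group.

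Nor does the working show an underpowered study. At the plan's own d, 20 per group keeps more than 80% power with 30% of cases misclassified. That depends on d = 1.53 being right and on few dropouts. The estimated difference would still be too small.

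Finally, the question and hypothesis speak of hypertension without the word controlled. This is editorial, since the PICOTS table and the second aim supply it.

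**Conclusion.** The point holds as a cheap improvement, not as a flaw that defeats the study. The documents themselves show that case status rests on an unverified statement which entry pressure cannot confirm, and that drug changes over the 3 months are not captured.

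The size is conditional. Between-group differences shrink to (1 - p) of their true value, or 90% to 70% for an assumed p of 10% to 30%. This takes misclassified cases to respond like controls and controls to be correctly labelled. The main harm is a biased estimate and a null result that is harder to interpret, more than lost power.

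The drug-change problem touches a secondary outcome only. It amounts to 0.5 to 3 mmHg under assumed shares and effects, and falls almost entirely in one group. It is enough to prevent a pressure change in cases from being attributed to NSPT.

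**What to change.** 1. In inclusion criterion 1, require the diagnosis to be confirmed by a medical record or a current antihypertensive prescription, noted at the case history already taken. For controls, require that there is no such diagnosis or prescription.
2. Make antihypertensive drugs a named item at baseline, and record any change by the 3-month visit. Report pressure change with and without patients whose drugs changed. That analysis may sit in the SAP, but the protocol has to collect the data.
3. Reconcile the pressure limits in section II, section VI and inclusion criterion 1.

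The cost is some protocol wording and two case-history items at existing visits. The downside is that a few self-reported patients without a record or prescription cannot be enrolled as cases.

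Two limits remain. A record would still admit a person once diagnosed and never treated, although the diagnosis itself would then be verified. Recording drugs removes one rival explanation for a pressure change but does not by itself establish NSPT as the cause, because both groups receive it.
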